6.3 Efficacy

Efficacy analyses are based on the efficacy analysis set by as-randomized treatment group only (excluding overall).

Treatment comparisons of binary endpoints are stratified by IWRS prophylactic migraine medication use at randomization except within subgroups. If a single cell has sparse data (< 5 subjects), then the analysis is performed pooled across strata.

All CIs are 2-sided. In treatment comparisons of binary endpoints, CIs are based on a normal approximation to the binomial distribution using asymptotic standard error (ASE). In descriptive analyses of binary endpoints, exact Clopper-Pearson CIs are used. Otherwise, CIs for continuous endpoints are based on the normal distribution.

Postdose efficacy data are slotted into analysis windows automatically by the eDiary (see Section 7.5.2). All efficacy endpoints are assessed using analysis windows, unless specified otherwise.

Methods of handling missing data in analyses of binary efficacy endpoints are defined as follows:

- Non-Completer = Failure (NC=F): Subjects with missing data at a single time point are classified as failures. This missing data imputation method is applied to endpoints based on data from a single time point (e.g., co-primary endpoints) as the main analysis method.
- Non-Completer with Missing Data at More than 1 Time Point = Failure (NC1=F): Subjects with missing data at > 1 time point postdose in a specified time period are classified as failures. This missing data imputation method is applied to endpoints that are based on data

from multiple time points (e.g., secondary endpoint of sustained pain freedom from 2 to 24 hours postdose) as the main analysis method.

- Non-Completer = Missing (NC=M): Subjects with missing data at a single time point are excluded from the analysis. This missing data exclusion method is applied to endpoints based on data from a single time point (e.g., co-primary endpoints) as a sensitivity analysis.
- Multiple imputation (see Section 6.3.2.1). This missing data exclusion method is applied only to the co-primary endpoints as a sensitivity analysis.
- Varying response rate imputation (see Section 6.3.2.1). This missing data exclusion method is applied only to the co-primary endpoints as a sensitivity analysis.

The intercurrent event of rescue medication use is handled using Rescue Medication = Failure (RM=F), i.e., subjects who take rescue medication are classified as failures for all efficacy assessments that are reported at or after taking rescue medication, i.e., (1) rescue medication start date/time \leq eDiary finding date/time if start time is not missing, or (2) rescue medication start date \leq eDiary finding date if start time is missing; see Sections 6.2.6.2 and 7.1). This method applies to all efficacy analyses, except the secondary endpoint of rescue medication use within 24 hours postdose.

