5 SAMPLE SIZE, POWER, AND TYPE 1 ERROR

It is anticipated that about 90% of the 700 subjects randomized to each treatment group will have a headache in the allotted time period, resulting in approximately 630 subjects evaluable for efficacy in each treatment group.

The sample size calculation is based on results from the Phase 2/3 dose-ranging study BHV3500-201. The response rates for the pooled zavegepant 10 mg and 20 mg groups, and for the placebo group in study BHV3500-201 were 22.8% and 15.5%, respectively, for pain freedom at 2 hours postdose, and 42.2% and 33.7%, respectively, for MBS freedom at 2 hours postdose.

A total sample size of 1,260 evaluable subjects (630 per treatment group) provides approximately 91% power for the co-primary endpoint of pain freedom at 2 hours postdose, approximately 88% power for the co-primary endpoint of MBS freedom at 2 hours postdose, and approximately 80% power to detect a difference between treatment groups for both endpoints jointly.

Type I error is controlled by a hierarchical gate-keeping procedure. First, the family of 2 co-primary endpoints is tested. In particular, zavegepant is tested for superiority against placebo at an alpha=0.05 level for both co-primary endpoints. If the tests of both co-primary endpoints are significant (i.e., both p-values are ≤ 0.05), then the secondary endpoints are tested hierarchically at the alpha=0.05 level in the order shown in the Section 3.1.2, using the efficacy analysis set. Thus, a secondary endpoint is tested only if the preceding secondary endpoint in the hierarchy is determined to be significant (i.e., p-value ≤ 0.05). If a test in the hierarchy is not significant, then any further tests on endpoints in the sequence have p-values presented only for descriptive purposes, and no conclusions are drawn from those results.

For exploratory endpoints, no attempt is made to adjust for multiplicity. Any exploratory endpoints for which p-values are produced are evaluated at an unadjusted, 2-sided alpha=0.05 level and presented only for descriptive purposes.

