The percentages of subjects with pain freedom at 2 hours postdose are compared between zavegepant and placebo using Cochran-Mantel-Haenszel (CMH) tests stratified by IWRS prophylactic migraine medication use at randomization (yes, no). In these analyses, the NC=F and RM=F methods are applied. The following statistics are presented:

- Response rate (i.e., “n/N” and percentage), ASE, and 95% CI by randomization stratum for each treatment group
- Response rate (i.e., “n/N” and percentage), ASE, and 95% CI for each treatment group
- Percentage difference between treatment groups (zavegepant – placebo), ASE, 95% CI, and p-value by randomization stratum
- Stratified percentage difference between treatment groups (zavegepant – placebo), ASE, 95% CI, and p-value.

The stratified percentage difference between zavegepant and placebo is tested at an alpha level of 0.05. Zavegepant is considered to be superior to placebo for this co-primary endpoint if the p-value for the stratified percentage difference is < 0.05.

The main analysis is repeated unstratified for each subgroup level of all efficacy subgroups of interest specified in Section 4.3.

Sensitivity Analyses

Sensitivity analyses include the following:

- Complete cases: The main analysis is repeated using NC=M, i.e., subjects who have missing pain intensity in the 2-hour postdose analysis window are excluded. First, the RM=F method of handling rescue medication use is applied. Next, subjects with missing pain intensity in the 2-hour analysis window are excluded. The same statistics as the main analysis are tabulated.

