6.3.4.1 Efficacy Outcomes over Time: Main Analyses

Efficacy outcomes are tabulated for the efficacy analysis set by treatment group as the number and percentage of subjects in categories (responder; failure; failure subcategories) at each time point from 15 minutes through 48 hours postdose. Subjects who are not classified as responders at a time point are classified as failures. Failure subcategories are mutually exclusive, because subjects who meet more than 1 failure criterion are classified according to the first failure criterion met; in case of ties, the first failure subcategory that is met in the specified hierarchy for an endpoint is chosen. Percentages for response rates are also shown with exact Clopper-Pearson 95% CIs.

Outcomes are presented separately for each of the following efficacy endpoints: pain freedom, MBS freedom, pain relief, nausea freedom, phonophobia freedom, photophobia freedom, and return to normal function. These analyses use the NC=F and RM=F methods to align with main analyses of co-primary and secondary endpoints (see Sections 6.3.2 and 6.3.3). Outcomes category nomenclature is as follows:

- “at time point” means in the analysis window of that postdose time point
- “No rescue medication taken at or before time point” means either (1) rescue medication start date/time missing, or (2) rescue medication start date/time $> \{eDiary \text{ finding date/time for the data assessment in the analysis window of that postdose time point}\}$
- “Rescue medication taken at or before time point” means either (1) rescue medication start date/time $\leq \{eDiary \text{ finding date/time for the data in the analysis window of that postdose time point}\}$, or (2) (rescue medication start date/time – study drug start date/time) \leq upper bound of the analysis window corresponding to that postdose time point (see Section 7.3), if the data are missing in the time point analysis window.

Outcomes for the efficacy analysis set are presented over time as described below. Subjects who are excluded from analyses have the following outcomes in by-subject listings:

- Subjects in the randomized analysis set who are not in the efficacy analysis set: “Not in the efficacy analysis set”
- Subjects in the efficacy analysis set with normal or missing functional disability level at the time of dosing for return to normal function: “Not evaluable: normal function at the time of dosing” or “Not evaluable: missing disability level at the time of dosing”

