Analyses are based on non-missing, postdose efficacy data relevant to each endpoint.

For a given time-to-event endpoint, subjects are considered to have an event through X hours ($X = 4$ or 8) if the first postdose eDiary finding date/time defining response is (1) at or before the upper bound of the X -hour analysis window in minutes (see Table 5), and (2) is before the imputed rescue medication start date/time, if not missing (see Section 7.1).

Otherwise, subjects who do not have an event through X hours are censored at the earliest of the following: (1) upper bound of the X -hour analysis window + 1 minute; (2) time from the study drug start date/time to the imputed rescue medication start date/time, if the time is at or before the upper bound of the X -hour analysis window in minutes; (3) time from the study drug start date/time to the last non-missing finding date/time defining the endpoint, if the time was before the lower bound of X -hour analysis window in minutes.

For each endpoint listed above, time to event is assessed by treatment group as follows:

- Kaplan-Meier plot and table using the following time intervals postdose: 0 to 15, >15 to 30, > 30 to 45, > 45 to 60, > 60 to 90, > 90 to 120, > 120 to 180, > 180 to 240, > 240 to 360, > 360 to 495, and > 495 minutes. The Kaplan-Meier plot displays the percentage of subjects with the event on the y-axis versus time in minutes on the x-axis.
- Time-to-event distribution table (minutes), including a log-rank p-value (zavegepant versus placebo).

See Section 6.1.1.1 for additional table and plot attributes.

6.3.4.4 *Efficacy Endpoints Compared over Time*

Treatment group comparisons of the percentage of subjects achieving response over time use analogous methods as the main analysis of the co-primary endpoint of pain freedom with NC=F and RM=F (see Section 6.3.2.1) for the efficacy analysis set and the following endpoints:

- Pain freedom
- Pain relief
- MBS freedom
- Return to normal function for subjects with functional disability at the time of dosing
- Phonophobia freedom for subjects with phonophobia present at the time of dosing
- Photophobia freedom for subjects with photophobia present at the time of dosing

- Nausea freedom for subjects with nausea present at the time of dosing.

For each endpoint and time point from 15 minutes through 48 hours postdose, the following are presented:

- Response rate (i.e., “n/N” and percentage), ASE, and 95% CI for each treatment group

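### SAP 6.3 uses normal-approximation intervals for binary comparisons; for arm-level rates these fail when responders are few or groups are small, and they duplicate the exact intervals planned for the same rates

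*SAP*

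**What the plan says.** SAP 6.3 sets the interval method for all binary efficacy endpoints: "In treatment comparisons of binary endpoints, CIs are based on a normal approximation to the binomial distribution using asymptotic standard error (ASE". The next sentence of that section assigns exact Clopper-Pearson intervals to descriptive analyses.

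The comparison method reaches further than the treatment difference:

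- SAP 6.3.2.1 tabulates a rate, its ASE and a 95% CI for each arm, overall and within each randomization stratum, together with the differences. It adds: "The main analysis is repeated unstratified for each subgroup level of all efficacy subgroups of interest specified in Section 4.3".
- SAP 6.3.3 carries the same methods to the secondary endpoints, including pain relief and return to normal function at 15, 30 and 60 minutes.
- SAP 6.3.4.4 applies them to seven endpoints over time: "For each endpoint and time point from 15 minutes through 48 hours postdose, the following are presented". The items listed include the arm-level rate with ASE and 95% CI.

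SAP 6.3.4.1 tabulates the same seven endpoints in the same analysis set, with the same missing-data and rescue rules and the same time points. There, "Percentages for response rates are also shown with exact Clopper-Pearson 95% CIs".

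SAP 6.3.4.2 gives exact intervals for complete-case rates. It states that its 2-hour pain and MBS freedom results equal the complete-case sensitivity analyses of 6.3.2.1 and 6.3.2.2, which use ASE intervals.

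Two provisions bear on sparse data. SAP 6.3 pools across strata when a cell has fewer than 5 subjects, and SAP 4.3 allows subgroup levels to be redefined or combined.

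**The concern.** The normal-approximation (Wald) interval is unreliable when the expected number of responders is small. That can happen at early time points, in a minority stratum (prophylactic medication use), or in a small subgroup level (race has Asian as a level of its own). Readers rely on the interval there to see how little is known. An interval of 0% to 0%, or one that starts below 0%, misstates that uncertainty while labelled 95%.

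The second issue does not depend on any assumption. One arm-level n/N receives two different 95% intervals, and the plan does not say which is to be quoted. The choice could then be made after unblinding.

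**Working it through.** **Inputs from the documents.** 630 evaluable per arm; planning rates 22.8% v 15.5% (pain freedom) and 42.2% v 33.7% (MBS freedom); alpha 0.05 (SAP 5); two-sided intervals (SAP 6.3, "All CIs are 2-sided"). **Assumed, because the documents give no figures:** low true rates of 0.2% to 5%, and group sizes of 10 to 100 per arm.

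**Step 1: reproduce the plan's power.** The documents state no coverage figure, so power is the available check on the inputs. Power = Φ[(Δ − 1.96·SE_pooled)/SE_unpooled].

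- Pain freedom: (0.073 − 1.96 × 0.02217)/0.02207 = 1.339, so 91.0% (stated 91%).
- MBS freedom: (0.085 − 1.96 × 0.02734)/0.02724 = 1.153, so 87.6% (stated 88%).
- Joint, as a product under independence: 0.910 × 0.876 = 79.6% (stated 80%).

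**Step 2: when the Wald limits fail.** The interval is p̂ ± 1.96·√[p̂(1 − p̂)/n]. With x = 0 the standard error is 0, so the width is 0. The lower limit is negative when x < 3.84(1 − p̂). With n = 630 that means 1 to 3 responders. In small groups it holds for 3 responders once n is 14 or more.

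| Responders/n | Wald 95% | Clopper-Pearson 95% |
|---|---|---|
| 0/630 | 0% to 0% | 0% to 0.58% |
| 3/630 | −0.06% to 1.01% | 0.10% to 1.39% |
| 0/90 | 0% to 0% | 0% to 4.0% |
| 1/10 | −8.6% to 28.6% | 0.3% to 44.5% |
| 144/630 | 19.6% to 26.1% | 19.6% to 26.3% |

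**Step 3: exact coverage, one arm.** For true rate π, coverage = Σ P(X = x; n, π) over all x whose interval contains π.

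| n per arm | True rate | Wald | Clopper-Pearson |
|---|---|---|---|
| 630 | 0.5% | 81.8% | 98.5% |
| 630 | 1% | 94.6% | 97.5% |
| 630 | 2% | 92.6% | 96.9% |
| 630 | 3% | 93.0% | 96.5% |
| 630 | 5% | 94.4% | 96.5% |
| 100 | 15.5% | 94.1% | 96.2% |
| 100 | 5% | 87.8% | 98.3% |
| 60 | 2% | 70.1% | 99.3% |
| 10 | 15.5% | 80.3% | 98.9% |

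At 60 per arm and 2%, the chance of a zero-width interval is 0.98^60 = 29.8%.

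**Step 4: exact coverage, unstratified difference.** The same enumeration over both arms.

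| n per arm | True rates | Wald | Newcombe |
|---|---|---|---|
| 630 | 0.5% v 0.2% | 94.7% | 98.8% |
| 630 | 1% v 0.5% | 94.5% | 96.1% |
| 630 | 22.8% v 15.5% | 95.0% | 95.0% |
| 100 | 2% v 1% | 86.0% | 99.1% |
| 20 | 22.8% v 15.5% | 94.5% | 95.2% |
| 10 | 22.8% v 15.5% | 90.0% | 96.8% |
| 10 | 42.2% v 33.7% | 92.2% | 95.3% |

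**Step 5: co-primary intervals at the planning rates.** Pain freedom: 7.3 ± 1.96 × 2.207 points gives 2.97 to 11.63 (Newcombe 2.96 to 11.62). MBS freedom: 3.16 to 13.84 (Newcombe 3.14 to 13.79). The change is negligible. The stratified CMH-weighted interval was not simulated.

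**Step 6: the overlapping tables.** 6.3.4.4 takes its definition of response from 6.3.4.1, so n and N are identical and only the interval method differs. In 6.3.4.2 the statement of sameness can be true of the rates but not of their intervals.

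**The case against.** The strongest reply is that the two methods are deliberate. SAP 6.3 separates comparisons from descriptive tables in adjacent sentences, and exact arm-level intervals are already planned at every time point. Sections 6.3.2.1 and 6.3.2.2 refer the 2-hour outcomes to 6.3.4.1 and repeat them by subgroup level, so exact intervals appear to be planned there too. This stands. A reader might infer that section 6.3 contradicts itself, and it does not. The result is duplication without a rule for which interval governs.

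A reader might also infer that treatment differences at early time points under-cover. Step 4 does not support that: at 630 per arm, coverage is 94.5% or higher for every pair tried, down to 0.5% v 0.2%.

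The low-rate figures are conditional. The early secondary endpoints are pain relief and return to normal function, and protocol 1.3.2 reports pain relief from 15 minutes in the earlier dose-ranging study, so rates near 0.5% are not established for them. The 70% figure needs a small stratum and a 2% rate together. Section 6.3.4.4 lists no by-stratum rows, so that combination could arise only for the early secondary endpoints.

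The sparse-cell rule helps to an extent that depends on an undefined term. If a cell means treatment by response, strata with fewer than 5 responders in an arm would be pooled. Merging subgroup levels can also help, but it is optional and has no threshold. Neither provision changes the interval method, and pooling strata cannot help a subgroup analysis that is already unstratified.

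**Conclusion.** The point holds as a low-cost improvement. It is not a threat to any confirmatory conclusion: superiority rests on the stratified p-values and the hierarchy, which are unaffected.

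Three things follow without assumptions. Arm-level ASE intervals have zero width at 0 responders, they usually have a negative lower limit at 1 to 3 responders, and they duplicate the exact intervals for the same rates.

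The size of the under-coverage is conditional on assumed rates and group sizes. For one arm of 630 it is clear at about 0.5%, modest at 2% to 3% and negligible from 5%. It is larger in small strata and subgroup levels. For differences it is confined to very small subgroups, or to small groups with very rare response. Strata of about 100 per arm at ordinary 2-hour rates are adequately covered.

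**What to change.** In SAP 6.3, specify Clopper-Pearson for every arm-level response rate: overall, by stratum, by subgroup level and in 6.3.4.4. Each n/N then has one interval, and the sameness statement in 6.3.4.2 becomes true of the intervals as well as the rates. Specify Newcombe or Miettinen-Nurminen intervals for unstratified differences in strata and subgroup levels. Leave the stratified CMH test and the stratified difference with its ASE interval as they are.

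The cost is SAP wording and option changes in programs that already produce exact intervals. Arm-level intervals become somewhat wider and slightly conservative (about 96% to 99% coverage in the cases above). Stratum differences would use a different method from the stratified difference in the same table, so the table needs a footnote naming both.

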6.3.1 Overall Efficacy

A by-subject listing of eDiary migraine characteristics is provided for the randomized analysis set that displays parameters listed in Section 7.5.2 at the time of dosing and over time postdose. The rescue medication start date/time and time to rescue medication use in hours are also included (see Sections 6.3.3.8 and 7.1); data collected on or after the rescue medication start date/time are identified.

6.3.1.1 Overall Summary of Primary and Secondary Endpoints

An overall summary of treatment comparisons of all primary and secondary endpoints tested hierarchically presents the following statistics:

- Response rate (i.e., “n/N” and percentage) and 95% CI for each treatment group
- Stratified percentage difference between treatment groups (zavegepant – placebo), 95% CI, and p-value.

Analyses are based on main methods described in Sections 6.3.2 and 6.3.3. Endpoints are displayed in the order presented in Sections 3.1.1 and 3.1.2. P-values that are determined to be significant based on the testing hierarchy are identified.

A forest plot of treatment comparisons of all primary and secondary endpoints tested hierarchically is produced for zavegepant versus placebo based on the overall summary. The plot displays the following statistics:

- Response rate (i.e., “n/N” and percentage) by treatment group

- Stratified percentage difference between treatment groups (zavegepant – placebo) and 95% CI.

Percentage differences with p-values that are determined to be significant based on the testing hierarchy are identified. Note that the plot displays results for *no* rescue medication use within 24 hours postdose and *no* pain relapse from 2 to 48 hours postdose so that positive percentage differences favor zavegepant for these secondary endpoints.

6.3.1.2 *Missing Efficacy Data*

Missing efficacy data are tabulated by treatment group as the number and percentage of subjects in the efficacy analysis set in the following categories:

- Missing pain intensity at each time point from 15 minutes through 48 hours postdose. These categories are not mutually exclusive because subjects may have missing pain intensity at multiple time points.
- Number of time points with missing pain intensity from 2 hours to 48 hours postdose: 0 (i.e., no missing pain intensity), 1, 2, 3, 4, 5, 6, 7. These categories are mutually exclusive.
- Missing data for the following efficacy parameters at 2, 24, and 48 hours postdose: pain intensity, nausea status, phonophobia status, photophobia status, and functional disability level.

In addition, missing pain intensity at 2 hours postdose are tabulated by subgroup level for each treatment group and overall for all subgroups specified in Section 4.3 plus the following subgroups:

- Pain intensity at the time of dosing (moderate or severe)
- MBS on study before dosing (nausea, phonophobia, or photophobia)
- Rescue medication use: yes, no.

6.3.2 *Primary Efficacy Endpoints*

Both co-primary efficacy endpoints are evaluated for the efficacy analysis set.

A by-subject listing of pain freedom and MBS freedom outcomes at each postdose time point is provided for the randomized analysis set that includes prophylactic migraine medication use at randomization, rescue medication start date/time (see Section 7.1), time to rescue medication start date/time in hours (see Section 6.3.3.8), pain intensity at the time of dosing, MBS on study before dosing, and reason for exclusion from the efficacy analysis set (see Section 6.2.1). See Section 6.3.4.1 for efficacy outcomes.

6.3.2.1 *Pain Freedom at 2 Hours Postdose*

Pain freedom at a single time point postdose is defined as having a pain intensity of none at that time point.

For the co-primary endpoint, subjects who meet both of the following criteria are classified as responders:

- Pain intensity of none at 2 hours postdose, i.e., in the 2-hour postdose analysis window
- No rescue medication taken at or before 2 hours postdose, i.e., (1) rescue medication start date/time missing, or (2) rescue medication start date/time > {eDiary finding date/time for the pain intensity assessment in the 2-hour postdose analysis window}.

Subjects who have any of the following are classified as failures:

- Rescue medication taken at or before 2-hours postdose (RM=F), i.e., (1) rescue medication start date/time \leq {eDiary finding date/time for the pain intensity assessment in the 2-hour postdose analysis window}, or (2) (rescue medication start date/time – study drug start date/time) \leq 135 minutes, the upper bound of the 2-hour postdose analysis window (see Section 7.3), if pain intensity is missing in the 2-hour postdose analysis window.
- Mild, moderate, or severe pain intensity at 2 hours postdose, i.e., in the 2-hour postdose analysis window
- Missing pain intensity at 2 hours postdose (NC=F), i.e., in the 2-hour postdose analysis window.

Main Analyses

Pain freedom outcomes at 2 hours postdose are tabulated by treatment group (see Section 6.3.4.1). Outcomes are tabulated analogously for each subgroup level of all efficacy subgroups of interest specified in Section 4.3.

The percentages of subjects with pain freedom at 2 hours postdose are compared between zavegepant and placebo using Cochran-Mantel-Haenszel (CMH) tests stratified by IWRS prophylactic migraine medication use at randomization (yes, no). In these analyses, the NC=F and RM=F methods are applied. The following statistics are presented:

- Response rate (i.e., “n/N” and percentage), ASE, and 95% CI by randomization stratum for each treatment group
- Response rate (i.e., “n/N” and percentage), ASE, and 95% CI for each treatment group
- Percentage difference between treatment groups (zavegepant – placebo), ASE, 95% CI, and p-value by randomization stratum
- Stratified percentage difference between treatment groups (zavegepant – placebo), ASE, 95% CI, and p-value.

The stratified percentage difference between zavegepant and placebo is tested at an alpha level of 0.05. Zavegepant is considered to be superior to placebo for this co-primary endpoint if the p-value for the stratified percentage difference is < 0.05.

The main analysis is repeated unstratified for each subgroup level of all efficacy subgroups of interest specified in Section 4.3.

Sensitivity Analyses

Sensitivity analyses include the following:

- Complete cases: The main analysis is repeated using NC=M, i.e., subjects who have missing pain intensity in the 2-hour postdose analysis window are excluded. First, the RM=F method of handling rescue medication use is applied. Next, subjects with missing pain intensity in the 2-hour analysis window are excluded. The same statistics as the main analysis are tabulated.
- Multiple imputation: The main analysis is repeated using the copy from reference multiple imputation approach with m=20 imputations to impute missing pain intensity at 2 hours postdose. The fully conditional specification (FCS) method is used with a generalized logit distribution. Covariates may include prophylactic migraine medication use at randomization (yes or no), sex, pain intensity at the time of dosing (moderate or severe), historical number of moderate to severe migraine attacks per month (< median, ≥ median), and MBS on study before dosing (nausea, phonophobia, or photophobia). First, the RM=F method of handling rescue medication use is applied. Next, missing response status (responder versus failure) in the 2-hour postdose analysis window is imputed for subjects who are not missing any of the covariates (subjects missing any of the covariates are considered failures). The same statistics as the main analysis are presented.
- Varying response rate imputation: The main analysis is repeated by imputing missing pain intensity at 2 hours postdose in each treatment group with varying response rates over the range of 0%, 10%, 20% and 30%. First, the RM=F method of handling rescue medication use is applied. Next, missing response status (responder versus failure) in the 2-hour postdose analysis window is imputed. The following statistics are presented: stratified percentage difference between treatment groups (zavegepant – placebo), ASE, 95% CI, and p-value.

